5.2.1. Analyses for Binary Data

Descriptive statistics for binary variables are the proportion (%) and the numerator (n) and the denominator (N) used in the proportion calculation. The 95% CI for percentage, and for the difference in percentages, will also be presented where applicable.

- 1. The 95% CI for the proportion (within vaccine group) will be constructed by the Clopper-Pearson method described by Newcombe.² The 95% CI will be presented in terms of percentage.
- 2. The 95% CI for the difference in the proportions (between vaccine groups) will be computed using the Miettinen and Nurminen method.³ The 95% CI will be presented in terms of percentage.

5.2.2. Analyses for Continuous Data

Unless otherwise specified, descriptive statistics for continuous variables are n, mean, median, standard deviation, minimum, and maximum.

The CI for the mean of the continuous variable will be constructed by the standard method based on the Student t distribution.

5.2.2.1. Geometric Means

Continuous immunogenicity endpoints will be logarithmically transformed for analysis. Geometric means and the associated 2-sided 95% CIs will be derived by calculating group means and CIs on the natural log scale based on the t distribution, and then exponentiating the results.

5.2.2.2. Geometric Mean Fold Rises

GMFRs will be calculated as the group mean of the difference of logarithmically transformed assay results (later time point minus earlier time point) and exponentiating the mean. GMFRs are limited to participants with nonmissing values at both time points. The associated 2-sided 95% CIs will be obtained by constructing CIs using the Student t distribution for the mean difference on the logarithm scale and exponentiating the confidence limits.

5.2.2.3. Geometric Mean Ratios

The GMRs will be calculated as the mean of the difference of logarithmically transformed assay results between 2 groups and exponentiating the mean. Two-sided CIs will be obtained by calculating CIs using the Student t distribution for the mean difference of the logarithmically transformed assay results and exponentiating the confidence limits.

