9.3.1.2.3. Geometric Mean Ratios

The GMRs will be calculated as the mean of the difference of logarithmically transformed assay results between 2 vaccine groups and exponentiating the mean. Two-sided CIs will be obtained by calculating CIs using the Student t distribution for the mean difference of the logarithmically transformed assay results and exponentiating the confidence limits.

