10.10.5. Objectives, Endpoints, and Estimands (Substudy B)

Substudy B

Objectives	Endpoints	Estimands	
Primary Safety	Primary Safety	Primary Safety	
To evaluate the safety profile of 2 formulations of combination RSVpreF + qIRV	 Local reactions (pain at the injection site, redness, and swelling) Systemic events (fever, fatigue, headache, vomiting, nausea, diarrhea, chills, new or worsened muscle pain, and new or worsened joint pain) AEs SAEs 	In participants receiving the study intervention, the percentage of participants reporting: • Local reactions within 7 days following vaccination • Systemic events within 7 days following vaccination • AEs throughout the study • SAEs throughout the study	
Secondary Immunogenicity	Secondary Immunogenicity	Secondary Immunogenicity	
To describe the immune responses elicited by 2 formulations of combination RSVpreF + qIRV	RSV A and RSV B NTs Strain-specific HAI titers for the current seasonal strains (2×A, 2×B) recommended by WHO for recombinant or cell-based influenza vaccines	In participants in compliance with the key protocol criteria (evaluable participants): GMT for each RSV subgroup (A or B) 1 month after vaccination with each formulation GMT of HAI titers for each strain included 1 month after vaccination with each formulation	

Substudy B

Objectives	Endpoints	Estimands
Exploratory	Exploratory	Exploratory
To further describe the immune responses elicited by 2 formulations of combination RSVpreF + qIRV	RSV A and RSV B NTs Strain-specific HAI titers	 In participants in compliance with the key protocol criteria (evaluable participants): GMTs of NTs for each RSV subgroup (A or B) before vaccination GMFRs of NTs for each RSV subgroup (A or B) from before vaccination to 1 month after vaccination GMTs of strain-specific HAI titers before vaccination GMFRs of strain-specific HAI titers from before vaccination to 1 month after vaccination The percentage of participants with strain-specific HAI titers ≥1:40 at each time point The percentage of participants achieving strain-specific HAI seroconversion^a 1 month after vaccination

a. Seroconversion is defined as an HAI titer <1:10 prior to vaccination and ≥1:40 at the time point of interest, or an HAI titer ≥1:10 prior to vaccination with a 4-fold rise at the time point of interest.

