2.2.3. SSB Secondary Estimands

2.2.3.1. SSB Secondary Immunogenicity Estimands

The secondary estimands for the RSV immunogenicity objective of Substudy B will use the hypothetical strategy and compare the RSVpreF immune response in participants without the intercurrent events. In other words, the immune response is estimated in the hypothetical setting where participants follow the study schedule and protocol requirements as directed. It includes the following 5 attributes:

- Treatment condition: 2 treatments applied: Combination (RSVpreF + qIRV) 1.0-mL and combination (RSVpreF + qIRV) 0.5-mL at Visit B101.
- **Population**: Adults ≥50 years of age, as defined by the study inclusion and exclusion criteria.
- Variables: RSV serum NTs and strain-specific HAI titers measured at 1 month after vaccination with combination (RSVpreF + qIRV) 1.0-mL at Visit B102 and 1 month after vaccination with combination (RSVpreF + qIRV) 0.5-mL at Visit B102.
- Intercurrent events: The intercurrent events listed in Section 2.2.1.1 and Section 2.2.1.2 could impact the interpretation or the measurement of the immune response.

The clinical question of interest is based on the comparison of the immune response elicited between combination (RSVpreF + qIRV) 1.0-mL group and 0.5-mL group, without any influence from any other immune-modifying drugs or vaccines and measured within a homogeneous time window. Therefore, all data after intercurrent events 1, 2, and 3, as well as all data at intercurrent event 4, if collected, will be excluded. Major protocol violations will be determined by clinical review (through the data-handling memo).

• Population-level summary: The group means measured as GMTs for each RSV subgroup (A or B) and GMT of HAI titers of each strain, for the combination RSVpreF + qIRV 1.0-mL group for 50-64 years, 65+ years and 50+ years; and combination (RSVpreF + qIRV) 0.5-mL group for 50-64 years, 65+ years and 50+ years separately.

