6. ANALYSES AND SUMMARIES

6.1. Primary Endpoint(s)

6.1.1. RSV A- and RSV B-Neutralizing Antibody Titers for Substudy A

6.1.1.1. Main Analysis

- Estimand strategy: Hypothetical (Section 2.2.1.1).
- Analysis set: Evaluable RSV immunogenicity population (Section 4).
- Analysis methodology: GMR, defined as the ratio of RSV A– and RSV B–neutralizing GMTs in the combination RSVpreF + qIRV group at Visit A102 to that in the sequential-administration RSVpreF group at Visit A103, will be summarized along with the 95% CI (Section 5.2.2.3).
- Intercurrent events: Data collected after an intercurrent event will not be included (Section 2.2.1.1).
- Missing data: Missing data will not be imputed (Section 5.3.2).
- RSV A- and RSV B-neutralizing GMTs and sample size in the combination group at Visit A102, and that in the sequential-administration RSVpreF group at Visit A103, will be presented.
- GMRs and 95% CIs for the GMRs, using the Student t distribution, will be presented (Section 5.2.2.3).
- Forest plots with GMRs and the 95% CIs will be presented.

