6.1.2. HAI Titers for Substudy A

6.1.2.1. Main Analysis

- Estimand strategy: Hypothetical (Section 2.2.1.2).
- Analysis set: Evaluable HAI immunogenicity population (Section 4).
- Analysis methodology: GMR, defined as the ratio of HAI GMTs in the combination RSVpreF + qIRV group to that in the sequential-administration qIRV group for each strain at Visit A102, will be summarized along with the 95% CI (Section 5.2.2.3).
- Intercurrent events: Data collected after an intercurrent event will not be included (Section 2.2.1.2).
- Missing data: Missing data will not be imputed (Section 5.3.2).
- HAI GMTs and sample size in the combination RSVpreF + qIRV group, and that in the sequential-administration qIRV group at Visit A102, will be presented.
- GMR and 95% CI for the GMR, using the Student t distribution, will be presented (Section 5.2.2.3).
- Forest plots with GMRs and the 95% CIs will be presented.

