6.2.1.1. Main Analysis

- Estimand strategy: Hypothetical (Section 2.2.1.1).
- Analysis set: Evaluable immunogenicity population (Section 4).
- Analysis methodology: GMR, defined as the ratio of RSV A– and RSV B–neutralizing GMTs in the 2 combination (RSVpreF + qIRV) 1.0-mL and 0.5-mL groups at Visit B102 will be summarized along with the 95% CI (Section 5.2.2.3).
- Intercurrent events: Data collected after an intercurrent event will not be included (Section 2.2.1.1).
- Missing data: Missing data will not be imputed (Section 5.3.2).
- RSV A- and RSV B-neutralizing GMTs and sample size in the 2 combination groups at Visit B102 will be presented overall and by age group.
- GMRs and 95% CIs for the GMRs, using the Student t distribution, will be presented (Section 5.2.2.3) overall and by age group.

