6.2.2. Secondary Endpoints for HAI Titers for Substudy B

6.2.2.1. Main Analysis

- Estimand strategy: Hypothetical (Section 2.2.1.2).
- Analysis set: Evaluable immunogenicity population (Section 4).
- Analysis methodology: GMR, defined as the ratio of HAI GMTs in the 2 combination (RSVpreF + qIRV) 1.0-mL and 0.5-mL groups at Visit B102 will be summarized along with the 95% CI (Section 5.2.2.3).
- Intercurrent events: Data collected after an intercurrent event will not be included (Section 2.2.1.2).
- Missing data: Missing data will not be imputed (Section 5.3.2).
- HAI GMTs and the sample size in the 2 combination groups at Visit B102 will be presented for each age group and overall.
- GMRs and 95% CI for the GMRs, using the Student t distribution, will be presented (Section 5.2.2.3) overall and by age group.

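### The Substudy A primary GMRs, and the GMRs the SAP adds in Substudy B, are valid but unadjusted: prevaccination titers and randomisation strata already collected are left out, which may cost precision

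*SAP*

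**What the plan says.** Protocol 9.3.1.2.3 gives the method: "The GMRs will be calculated as the mean of the difference of logarithmically transformed assay results between 2 vaccine groups and exponentiating the mean". SAP 5.2.2.3 repeats it almost word for word: "The GMRs will be calculated as the mean of the difference of logarithmically transformed assay results between 2 groups and exponentiating the mean". In both, the interval is a Student t interval on the log scale, with no covariate or stratum term.

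- **Substudy A.** SAP 6.1.1.1 (RSV) and 6.1.2.1 (HAI) apply this method to the primary estimands. For HAI: "GMR and 95% CI for the GMR, using the Student t distribution, will be presented". For RSV, the display also includes the "GMTs and sample size in the combination group at Visit A102" and the matching Visit A103 values for the sequential group, all raw.
- **Substudy B.** The protocol's secondary estimand (10.10.5) is a per-group summary: "GMT for each RSV subgroup (A or B) 1 month after vaccination with each formulation". SAP 2.2.3.1 agrees: "The group means measured as GMTs for each RSV subgroup (A or B) and GMT of HAI titers of each strain". Protocol Table 9 contains no GMR. SAP 6.2.1.1 adds one: "GMRs and 95% CIs for the GMRs, using the Student t distribution, will be presented (Section 5.2.2.3) overall and by age group". SAP 6.2.2.1 does the same for HAI.
- **Supplementary analyses.** The mITT analyses keep the same presentation.

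Protocol 10.9.10.1 and 10.10.10.1 plan prevaccination RSV and HAI titers for all participants. Randomisation is stratified by three age groups in Substudy A (10.9.6.1) and six age/sex groups in Substudy B (10.10.6.1). Fold rises, seroconversion and age-group displays use baseline or age, but none of them adjusts the GMR. SAP 6.3 is redacted and is not counted either way.

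**The concern.** Prevaccination titer is often correlated with postvaccination titer. If it is here, an unadjusted difference of means carries variance that a model could remove, using data the study collects anyway.

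This matters most in Substudy A. SAP 5.1 sets no hypothesis and no decision rule, so the GMR and the width of its interval are all a reader has for judging interference on the primary immunogenicity objective. In Substudy B the point is minor overall. It carries more weight for the by-age GMRs, which rest on about 50 participants per formulation.

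**Working it through.** **Inputs.** From protocol 10.9.11.5: 110 evaluable per group, true GMR 1, natural-log SD 1.3 (RSV A), 1.4 (RSV B) and 1.24 (each influenza strain), and a 2-fold margin. Level: two-sided 95%. Assumed, because the documents give no value: the correlation r between log baseline and log postvaccination titer.

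**1. Reproduce the plan's figures.** For an unadjusted two-sample t interval with pooled variance, SE = SD × sqrt(2/110). The probability that the lower bound falls below 0.5 is the noncentral t distribution function at t(0.975; 218), with df 218 and ncp = ln 2 / SE. For RSV B, SE = 1.4 × sqrt(2/110) = 0.1888 and ncp = 0.6931/0.1888 = 3.67.

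| Antigen | Stated | Reproduced |
|---|---|---|
| RSV A | 2.4% | 2.40% |
| RSV B | 4.5% | 4.50% |
| Influenza | 1.5% | 1.51% |

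The match fits an unadjusted method. The SAP does not name the variance form; pooled variance is inferred from the common-SD column.

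**2. Validity.** In a 5,000-run simulation with stratified allocation, the unadjusted interval covered 95.0-95.2% and the adjusted one 94.3-95.0%.

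**3. Gain and cost of adjusting.** Residual SD is SD × sqrt(1 - r²). The expected cost of k extra terms is sqrt(1 + k/(2n - k - 3)) times the ratio of t quantiles. For Substudy A (k = 3: baseline plus two age terms) this is sqrt(1 + 3/214) × 1.0001 = 1.0071. The net width ratio is sqrt(1 - r²) × 1.0071.

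| r | Net width ratio | RSV B net P(LB<0.5) |
|---|---|---|
| 0 | 1.007 | 4.75% |
| 0.3 | 0.961 | 3.25% |
| 0.5 | 0.872 | 1.28% |
| 0.6 | 0.806 | 0.50% |

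The probabilities use df 215 and the SE inflated by sqrt(1 + 3/214).

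**4. RSV in Substudy A.** The combination endpoint is one month after A101; the sequential endpoint (A103) is about two months after it, with qIRV and RSVpreF in between. Correlation may therefore be weaker in the sequential group. With equal group sizes and variances and a common slope, residual variance is 1 - ((r1 + r2)/2)². RSV B at observed GMR 1:

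| r by group | Net width ratio | 95% CI | P(LB<0.5) |
|---|---|---|---|
| Unadjusted | 1 | 0.69-1.45 | 4.5% |
| 0.3 and 0.1 | 0.987 | 0.69-1.44 | 4.05% |
| 0.5 and 0.1 | 0.961 | 0.70-1.43 | 3.25% |

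**5. HAI in Substudy A.** Both groups are measured at A102, so a common r is more plausible. With SD 1.24 at GMR 1, the unadjusted interval is 0.72-1.39. By the step 3 formula it is 0.73-1.37 at r = 0.3 and 0.75-1.33 at r = 0.5.

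**6. Substudy B.** SD 1.4 is borrowed from Substudy A and everyone is taken as evaluable (assumptions).

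- Overall, n = 100 per group: 0.677-1.478 unadjusted. With k = 6 the cost is 1.6%, and the net interval at r = 0.5 is 0.709-1.410.
- One age group, n = 50: 0.574-1.743 unadjusted. With k = 2 the cost is 1.1%, and the net interval at r = 0.5 is 0.615-1.626. With k = 4 (≥65 years, ≥80 cells not pooled) the cost is 2.2%.

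**7. Break-even.** If strata explain nothing, adjustment pays once r exceeds sqrt(1 - 1/(1 + cost)²): about 0.12 in Substudy A, 0.18 in Substudy B overall, and 0.15-0.21 by age group.

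**The case against.** The strongest reply is that this is a preference. Both substudies are descriptive Phase 1b work, no passage promises an adjusted analysis, and the protocol's own benchmark (under 5% chance of a lower bound below 0.5) is met without one. The gain rests wholly on an assumed r, and the range includes a slight loss. For RSV, 0.69-1.45 against 0.69-1.44 would change nobody's reading. The RSV SDs are also the largest seen in an earlier study, so the absolute figures are conservative: with SD 1.2 (assumed) the unadjusted RSV probability would already be about 1.1%.

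All of that stands as a limit on size. It does not remove the point, because the worst expected cost in Substudy A is about 0.7% of interval width and no new data are needed. The reply is also right that ANCOVA brings choices of its own (pooling, missing baseline, values below LLOQ). These have to be settled in advance.

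A reader might infer more: that the planned intervals are wrong, that stratified randomisation makes the t interval invalid, or that the sample-size table is in error. The documents support none of these. Coverage is correct and the table reproduces. Nor is the Substudy B GMR an estimand that has been mis-analysed; there it is only a method added in the SAP.

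**Conclusion.** The point holds as one of efficiency. The planned GMRs are valid but leave baseline titer and strata unused, and so may give up precision. No planned decision changes.

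In Substudy A the net change in log-scale interval width runs from 0.7% wider (r = 0) to 19% narrower (r = 0.6). That range applies mainly to HAI; for RSV 1-4% narrower is a realistic expectation under the by-group correlations shown. The Substudy B gain at a given r is similar, but the GMR is less central there. Everything beyond the reproduced table depends on the assumed r; the RSV B figures also use the conservative SD of 1.4.

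**What to change.** Add to the SAP a prespecified ANCOVA on log titer with:

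- **Terms.** Vaccine group, prevaccination log titer of the same antigen or strain, and randomisation stratum.
- **Baseline.** A101 in both Substudy A groups and B101 in Substudy B. State that A101 differs on purpose from the A102 baseline that SAP 3.4.2.1 prefers for the sequential-group RSV fold rise, since A102 follows randomisation and qIRV.
- **Sparse strata.** Pool ≥80 with 65-79 by a rule fixed in advance and blind to titers: always, or below a stated cell count.
- **Missing or low baseline.** Set a missing baseline to the mean pooled across groups, as a stated exception to the no-imputation rule in SAP 5.3.2, so that evaluable participants are kept. Set values below LLOQ to 0.5 × LLOQ, as that section already does.
- **By-age GMRs in Substudy B.** Baseline plus only the strata left within that age group.
- **Display.** Model-based GMTs beside the adjusted GMR; keep the raw GMTs and the unadjusted GMR.

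Make this the main Substudy A analysis only if it is fixed before titers are summarised by group. Section 9 of the protocol then calls for an amendment, here to 9.3.1.2.3. Some sponsor staff are unblinded (10.9.8.2.3) and data may be summarised as they become available (10.9.11.4.1), so that option may close early; the documents do not show whether it has. Otherwise make it supplementary, which needs only a SAP update. A SAP update is also enough for Substudy B, where the GMT per formulation stays the estimand summary.

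The cost is a few extra rules and, if the covariates explain nothing, intervals about 0.7% wider in Substudy A, 1.6% in Substudy B overall and 1.1-2.2% by age group. No visits, samples or assays are added.

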5.2.2.4. Reverse Cumulative Distribution Curves

Empirical RCDCs will plot proportions of participants with values equal to or exceeding a specified assay value versus the indicated assay value, for all observed assay values. Data points will be joined by a step function with the line first going down and then to the right to the next assay value.

5.3. Methods to Manage Missing Data

5.3.1. Safety Data

Standard algorithms for handling missing AE dates and missing AE severity will be applied as described in the safety rulebook summary.

Missing data-handling rules on the safety data are described in detail in the corresponding endpoint sections.

5.3.1.1. Reactogenicity Data

For derived variables based on reactogenicity data, if any day of the 7-day e-diary is available, the "any day (Day 1 through Day 7)" data will be considered nonmissing.

The reactogenicity data are collected through the e-diary, which does not allow participants to skip the question. Therefore, for a specific day, if the e-diary data are transferred for that day, all of the reactogenicity data for the participant on that day are nonmissing. No missing reactogenicity data will be imputed other than what is described in Section 3.1.3. In summary, for any participant with all 7 days of the e-diary missing, this will not be included in the analysis (ie, assuming MCAR).

DMB02-GSOP-RF02 7.0 Statistical Analysis Plan Template 31-Jan-2022 PFIZER CONFIDENTIAL TMF Doc ID: 98.03 Page 35 of 46 Based on data from available studies, the missing data for reactogenicity are minimal, which is consistent with Li et al.⁴ No sensitivity analysis is planned for reactogenicity data.

5.3.2. Immunogenicity Data

Any assays above LLOQ are considered accurate and their quantitated values will be reported. Values below the LLOQ, or denoted as BLQ, will be set to $0.5 \times$ LLOQ for analysis.

For calculating a fold rise, < LLOQ will be converted to 0.5 \times LLOQ for a numerator, and < LLOQ will be converted to LLOQ for a denominator when only 1 of either the numerator or denominator is < LLOQ. If both the numerator and denominator are < LLOQ, then both will be converted in the same way.

The LLOQs for each assay will be included in the final released assay data.

Values for sera that are QNS, indeterminate results, or values recorded as "not done" will be set to "missing." Additionally, any time point with no blood draws will not be included in the analysis. No imputation will be done for these missing values, as MCAR is assumed for immunogenicity data according to Scott and Hsu.⁵

6. ANALYSES AND SUMMARIES

6.1. Primary Endpoint(s)

6.1.1. RSV A- and RSV B-Neutralizing Antibody Titers for Substudy A

6.1.1.1. Main Analysis

- Estimand strategy: Hypothetical (Section 2.2.1.1).
- Analysis set: Evaluable RSV immunogenicity population (Section 4).
- Analysis methodology: GMR, defined as the ratio of RSV A– and RSV B–neutralizing GMTs in the combination RSVpreF + qIRV group at Visit A102 to that in the sequential-administration RSVpreF group at Visit A103, will be summarized along with the 95% CI (Section 5.2.2.3).
- Intercurrent events: Data collected after an intercurrent event will not be included (Section 2.2.1.1).
- Missing data: Missing data will not be imputed (Section 5.3.2).
- RSV A- and RSV B-neutralizing GMTs and sample size in the combination group at Visit A102, and that in the sequential-administration RSVpreF group at Visit A103, will be presented.
- GMRs and 95% CIs for the GMRs, using the Student t distribution, will be presented (Section 5.2.2.3).
- Forest plots with GMRs and the 95% CIs will be presented.

6.1.1.2. Supplementary Analysis

To support the assessment of immunogenicity, estimands as specified in Section 2.2.4, using the treatment policy strategy, will be summarized with the mITT immunogenicity population using the same presentation (except the forest plots) as specified in the main analysis.

6.1.2. HAI Titers for Substudy A

6.1.2.1. Main Analysis

- Estimand strategy: Hypothetical (Section 2.2.1.2).
- Analysis set: Evaluable HAI immunogenicity population (Section 4).
- Analysis methodology: GMR, defined as the ratio of HAI GMTs in the combination RSVpreF + qIRV group to that in the sequential-administration qIRV group for each strain at Visit A102, will be summarized along with the 95% CI (Section 5.2.2.3).
- Intercurrent events: Data collected after an intercurrent event will not be included (Section 2.2.1.2).
- Missing data: Missing data will not be imputed (Section 5.3.2).
- HAI GMTs and sample size in the combination RSVpreF + qIRV group, and that in the sequential-administration qIRV group at Visit A102, will be presented.
- GMR and 95% CI for the GMR, using the Student t distribution, will be presented (Section 5.2.2.3).
- Forest plots with GMRs and the 95% CIs will be presented.

